## **16 Prior Medications and Concomitant Medications**

Prior and concomitant medications will be presented for SS, and coded using WHO Drug Global Dictionary: XXXX.

- Concomitant medication will be listed and summarized by Anatomical Therapeutic Chemical (ATC) level 3 and preferred chemical substance, a listing will be presented for prior medication. If a patient had more than one concomitant medication within ATC, the patient will be counted only once within a ATC Term.
- Prior medications are medications that started and stopped prior to the first application of study device within the observation.
- Concomitant medications are medications which are ended on or after the date of the first application of study device within the observation or were ongoing at the end of the study.
- The medication will be regarded as concomitant medication, if medication and concomitant medication cannot be classified according to the relationship between the date of first application of study device and the end date of a medication.

## **17 Efficacy Analysis**

The analysis of primary endpoints will be based on the PPS. Sensitivity analysis of the primary endpoints and analysis of secondary endpoints will be based on the FAS. All the efficacy endpoints will be assessed at the mid-week treatment day dialysis session.

## 17.1 Primary Efficacy

### 17.1.1 Primary Efficacy Variables & Derivations

Primary efficacy endpoints:

The reduction ratios of  $\lambda$  FLC and  $\beta 2$ -MG at the mid-week treatment day dialysis session.

Derivations of analysis variables:

$$\text{Reduction ratio (unit: \%)} = (1 - \frac{C_{\text{Post}}}{C_{\text{Pre}}}) \times 100\%$$

$C_{\text{Pre}}$  and  $C_{\text{Post}}$  are the measured arterial plasma concentrations of the solute before and after the mid-week treatment day dialysis session, respectively.

However, for the middle molecules ( $\lambda$  FLC and  $\beta 2$ -MG)  $C_{\text{Post}}$  will be first corrected ( $C_{\text{Post-corr}}$ ) for the decrease in total extracellular volume due to fluid removal as follows:

$$C_{\text{Post-corr}} = \left( \frac{c_{\text{post}}}{1 + \frac{BWP_{\text{Pre}} - BWP_{\text{Post}}}{0.2 \times BWP_{\text{Post}}}} \right)$$

$C_{\text{Post}}$  is the measured plasma concentration of the solute after dialysis; and  $BWP_{\text{Pre}}$  and  $BWP_{\text{Post}}$  are the patient's body weight before and after dialysis, respectively.

Data of the variables above will be collected from the Central Lab .

### 17.1.2 Primary Analysis Of Primary Efficacy Variables

PPS population is the primary efficacy analysis population. Descriptive statistics of reduction ratios of  $\lambda$  FLC and  $\beta 2$ -MG will be provided by treatment group.

Listings of reduction ratio will be presented and sorted by patient id and treatment group.

The statistical hypothesis for testing the treatment group difference for reduction ratios of  $\lambda$  FLC is presented as follows:

- $H_0: \mu_T - \mu_R \leq -3.783$  tested against the alternative hypothesis
- $H_a: \mu_T - \mu_R > -3.783$

where:

$\mu_T$  is the means of RRs of  $\lambda$  FLC in Theranova 400 treatment and  $\mu_R$  is the means of RRs of  $\lambda$

FLC in the FX 800 treatment.

A two-sample t-test will be utilized to generate a two-sided 95% confidence interval (CI) for the difference in means ( $\mu_T - \mu_R$ ). If the lower bound of the CI is greater than -3.783, then non-inferiority between the Theranova 400 and FX 800 treatment group can be demonstrated for  $\lambda$  FLC RR. If the lower bound of the CI is greater than zero, then superiority of Theranova 400 treatment over FX 800 treatment can be concluded.

The statistical hypothesis for testing the treatment group difference for reduction ratios of  $\beta 2$ -MG is presented as follows:

- $H_0: \mu_T - \mu_R \leq -7.848$  tested against the alternative hypothesis
- $H_a: \mu_T - \mu_R > -7.848$

where:

$\mu_T$  is the means of RRs of  $\beta 2$ -MG in Theranova 400 treatment and  $\mu_R$  is the means of RRs of  $\beta 2$ -MG in the FX 800 treatment.

A two-sample t-test will be utilized to generate a two-sided 95% confidence interval (CI) for the difference in means ( $\mu_T - \mu_R$ ). If the lower bound of the CI is greater than -7.848, then non-inferiority between the Theranova 400 and FX 800 treatment group can be demonstrated for  $\beta 2$ -MG RR. If the lower bound of the CI is greater than zero, then superiority of Theranova 400 treatment over FX 800 treatment can be concluded.

The two hypothesis tests are hierarchically structured so that the second test (superiority) will only be considered if the first test (non-inferiority) is rejected. There is no alpha adjustment for the second test as a result of the hierarchical testing.

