### 7.1.6.2 Method for Evaluation, Recording and Analysis of Efficacy Endpoints and Time Selection

#### 7.1.6.2.1 Evaluation Methods

##### (1) Reduction ratio (RR):

The RR for each solute, based on the change in the arterial plasma concentration over the dialysis session, will be calculated as:

$$RR(\%) = (1 - \frac{C_{post}}{C_{pre}}) \times 100\%$$

Where  $C_{pre}$  and  $C_{post}$  are the measured arterial plasma concentrations of the solute before and after dialysis, respectively [17].

However, for the middle molecules ( $\lambda$  FLC,  $\kappa$  FLC,  $\alpha 1$ -MG, CFD, YKL-40, myoglobin and  $\beta 2$ -MG)  $C_{post}$  will be first corrected ( $C_{post-corr}$ ) for the decrease in total extracellular volume due to fluid removal as follows:

$$C_{post-corr} = \left( \frac{C_{post}}{1 + \frac{BW_{pre} - BW_{post}}{0.2 \times BW_{post}}} \right)$$

Where  $C_{post}$  is the measured plasma concentration of the solute after dialysis; and  $BW_{pre}$  and  $BW_{post}$  are the patient's body weight before and after dialysis, respectively [18].

(2)  $spKt/V_{urea}$  refers to single pool  $Kt/V$ . The single pool  $Kt/V$  will be calculated as [1]:

$$spKt/V_{urea} = -\ln[\frac{\text{post dialysis Urea}}{\text{pre dialysis Urea}} - 0.008 \times \text{total dialysis time(h)}] + [4 - 3.5 \times \frac{\text{post dialysis Urea}}{\text{pre dialysis Urea}}] \times$$

$$\frac{\text{ultrafiltration volume (in liters)}}{\text{post dialysis Weight}}$$

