## 7.2 Study Process

### 7.2.1 Study Flow

#### 7.2.1.1 Study Flowchart and Schedule of Events

**Figure 2: Study Flowchart**

#### Schedule of Events:

Content of visit	Screening Period		Randomization	Enrollment	Visit 1 (Note: Must be conducted in 2 weeks after randomization)		
	Day -14~	Day -1			Mid-week 1		
	Pre- regular Dialysis	Post- regular Dialysis	Pre- Intervention Dialysis (Theranova/ HDF)	Post-Intervention Dialysis (Theranova/ HDF)	Follow-Up		
ICF	X						
Inclusion/Exclusion criteria	X						
Demographics 	X						
Medical history 	X						

Previous dialysis treatment parameters 	X						
Laboratory tests (Clinical Laboratory of Study Center)							
Coagulation function 	X						
Blood glucose, cholesterol, triglyceride;	X						
Hepatitis B surface antigen, Hepatitis C virus antibody, HIV, syphilis;	X						
Pregnancy blood test 	X						
Liver function 	X				X		
Blood routine 	X				X	X	
Serum Creatinine	X				X	X	
Blood urea nitrogen/Blood urea	X	X			X	X	
CRP	X				X		
Electrolytes 	X				X	X	
Laboratory tests (Central laboratory)							
$\beta$ 2-MG					X	X	
$\alpha$ 1-MG					X	X	
$\lambda$ FLC					X	X	
$\kappa$ FLC					X	X	
YKL-4					X	X	
CFD					X	X	
Myoglobin					X	X	
Serum Albumin					X		
Others							
Vital signs 	X			X	X	X	
Pre-dialysis and post-dialysis body weight, dry weight	X	X			X	X	
Treatment parameters 					X		
Device Deficiencies 					X	X	
Adverse Events	X	X	X	X	X	X	X
Previous/Concomitant medication	X 	X		X	X	X	

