## 3.2 Sample Size Calculation

### 3.2.1 Total Sample Size

The goal of this study is to demonstrate non-inferiority of Theranova 400 compared to FX 800 in the 2 primary endpoints and the non-inferiority margins selected are considered clinically acceptable. The sample size calculation is performed using PASS procedure Mann-Whitney U or Wilcoxon Rank-Sum Tests for Non-Inferiority. A separate sample size calculation is performed for both primary endpoints using a specified non-inferiority margin of 10% and a one-sided alpha level of 0.025, where the true difference in means is assumed to be zero (0).

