### 3.2.2 Sample Size Calculation In Regard To $\lambda$ FLC Reduction Ratio

A previously conducted Theranova HDF study was used to obtain  $\lambda$  FLC RR mean and standard deviation (SD) of 37.83 and 8.26; a higher estimate for SD of 9.09 is used by adding an additional +10% error to calculate sample size to account for a potential increase in variability. Based on a 1:1 randomization, with a sample size of 129 patients in the Theranova 400 group and 129 patients in the FX 800 group (total N = 258), a Wilcoxon Rank-Sum test with a 0.025 one-sided significance level will have 90% power to demonstrate non-inferiority of the Theranova 400 Dialyzer compared to the FX 800 Dialyzer as assessed by  $\lambda$  FLC RR with a non-inferiority margin of 10% (i.e. 3.783).

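### Adjusting the deciding analysis of both co-primary reduction ratios for screening dry weight, already collected, would narrow the CI without new patients; the unadjusted t-test is valid and the size of the gain is unknown

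*SAP*

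**What the plan says.** - **Deciding analysis.** Protocol 8.7.1.1 and SAP 17.1.2 treat lambda FLC and beta2-MG alike: "A two-sample t-test will be utilized to generate a two-sided 95% confidence interval (CI) for the difference in means". There is no other term. Non-inferiority needs a lower bound above -3.783 and -7.848 points respectively. Both endpoints must pass (SAP 8.2), on the per-protocol set.
- **Adjusted models.** Sensitivity 1 (SAP 17.1.3) has treatment and site only. In Sensitivity 3, step 1 names age, gender, creatinine and BUN as predictors for missing baseline values; step 2, which fills in the remaining missing data, names no covariates.
- **Weight data.** The schedule of events lists "Pre-dialysis and post-dialysis body weight, dry weight" at screening and again at Visit 1. Its note 3 records QB and dry weight with the last six prescriptions. SAP 14 only tabulates these.
- **Weight inside the endpoint.** Post-dialysis concentrations are corrected "for the decrease in total extracellular volume due to fluid removal as follows" (protocol 7.1.6.2.1), with a term of 0.2 x post-dialysis body weight.
- **Sizing.** SAP 3.2.1 uses "a one-sided alpha level of 0.025" and a true difference of zero. For lambda FLC (SAP 3.2.2), "a higher estimate for SD of 9.09 is used by adding an additional +10% error", and 129 per arm "will have 90% power to demonstrate non-inferiority" with a margin of 3.783.

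**The concern.** By mass balance, the RR after one session depends on clearance x time / distribution volume. Each arm uses one dialyzer model and protocol 7.2.1.3 sets a single treatment time, so unless clearance rises in step with body size, larger patients will tend to have lower RRs. The weight term in the endpoint formula corrects for fluid removed during the session; it does not standardise RR for body size.

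If so, part of the between-patient variance is predictable from a value known before randomisation, and the t-test leaves it in the error term. What is at stake is CI width, mainly for lambda FLC, which drives the sample size, and for the superiority step.

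**Working it through.** **1. The plan's figures reproduce.** Normal approximation for lambda FLC: n per arm = 2 x (1.960 + 1.282)^2 x (9.09/3.783)^2 = 121.3, so 122. The noncentral t gives 123. Dividing by the Wilcoxon relative efficiency 3/pi = 0.955 gives 123/0.955 = 128.8, so **129**. For beta2-MG (SD 14.28, margin 7.848): 71/0.955 = 74.35, so **75**. With 5% loss: 258/0.95 = 271.6, so **272**.

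**2. The t-test as planned, 129 per arm.** For lambda FLC, SE = 9.09 x sqrt(2/129) = 1.132 and half-width = 1.969 x 1.132 = 2.23 points. Power is about 91.5% (3.783/1.132 - 1.969 = 1.37 on the normal scale). For beta2-MG the half-width is 3.50 points and power 99.3%.

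**3. Gain for a given correlation.** With one baseline covariate, residual SD = SD x sqrt(1 - rho^2). The documents give no rho, so a range is assumed. Lambda FLC, 129 per arm:

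| Assumed abs(rho) | CI width ratio | Half-width | Power | n per arm for 90% (t) |
|---|---|---|---|---|
| 0 | 1.000 | 2.23 | 91.5% | 123 |
| 0.1 | 0.995 | 2.22 | 91.7% | 122 |
| 0.2 | 0.980 | 2.18 | 92.5% | 118 |
| 0.3 | 0.954 | 2.13 | 93.7% | 112 |
| 0.4 | 0.917 | 2.04 | 95.3% | 103 |
| 0.5 | 0.866 | 1.93 | 97.0% | 92 |
| 0.6 | 0.800 | 1.78 | 98.6% | 79 |

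**4. Which rho is plausible?** Assume RR = 100 x (1 - exp(-k)), with k = Kt/V and V proportional to dry weight. The planned means of 37.83 and 78.48 (protocol 8.5) give k = -ln(1 - 0.3783) = 0.475 and k = -ln(1 - 0.7848) = 1.536. The slope per unit of ln V is 100 x k x exp(-k), that is 29.5 points for lambda FLC and 33.1 for beta2-MG. A 10% difference in volume then moves the RR by about 3.0 and 3.3 points.

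Simulated CI width ratios (3,000 trials per scenario, 129 per arm, planned SDs), for an assumed weight CV of 10 / 15 / 20%:

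| | Clearance independent of weight | Clearance rises with square root of weight |
|---|---|---|
| Lambda FLC | 0.95 / 0.88 / 0.77 | 0.99 / 0.97 / 0.95 |
| Beta2-MG | 0.975 / 0.94 / 0.89 | 0.995 / 0.99 / 0.975 |

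Simulated one-sided type I error at the margin was 0.022 to 0.030 with or without adjustment (Monte Carlo SE about 0.003).

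**5. Check on the upper end.** With clearance independent of weight and CV 20%, the weight-driven SD of beta2-MG RR is 33.1 x 0.20 = 6.6 points. The total SD in the earlier study was 6.75 (SAP 3.2.3), so weight alone would explain (6.6/6.75)^2, about 96% of the variance. At CV 15% the share is (4.96/6.75)^2 = 54%. That study's weight spread is not given, but 96% is hard to credit for one covariate.

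**6. Cost in degrees of freedom.** Dry weight uses one of 256. With the 11 institutions of protocol 5.5, a model with treatment, site and dry weight has 1 + 1 + 10 + 1 = 13 parameters and 258 - 13 = 245 degrees of freedom. The t quantile moves from 1.969 to 1.970.

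**The case against.** The strongest reply is that nothing is broken: the t-test is valid under randomisation, type I error is held, and power exceeds its 90% target. All of that stands.

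A reader might infer more than the documents support:

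- **That chance imbalance in body size biases the result.** It does not. With clearance independent of weight it adds 29.5 x CV x sqrt(2/129), or 0.37 to 0.74 points at CV 10% to 20%, to the sampling SD of the lambda FLC difference. The unadjusted CI already allows for this. Adjustment removes the variation; it corrects no bias.
- **That the CI is known to be much too wide.** The inputs are assumptions. QB and QD are set only as minimums (protocol 7.2.1.3), so clearance may rise with body size, and the Kt/V entry criterion above 1.2 tends to exclude patients with a large volume for their clearance. Both weaken the correlation, and the gain could be about 1% or less.
- **That the protocol itself states the kinetic relation.** The factor 0.2 x weight appears only in the fluid-removal correction.
- **That the RR imputation model is fixed without weight.** The SAP gives its covariate list only for missing baseline values.
- **That note 10 supplies pre-randomisation QB.** It describes Visit 1; only note 3 covers earlier sessions.

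A further reply is that changing protocol 8.7.1.1 would need Ethics Committee re-approval (protocol 14.3). SAP section 4 already records two departures from the protocol's analysis, so the same route is available here.

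**Conclusion.** The point holds as an efficiency improvement and not as an error. The deciding analysis leaves out a plausible predictor of RR that is measured before randomisation at no extra cost. The gain cannot be derived from the documents: 0.5% to 20% narrower for |rho| 0.1 to 0.6. For lambda FLC at weight CV 10% to 20%, it is about 1% to 5% if clearance rises with the square root of weight and about 5% to 23% if clearance is independent of weight, with the upper end doubtful. These figures assume single-pool kinetics and volume proportional to dry weight. For beta2-MG the gain matters little for non-inferiority, since power is already 99.3%.

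The margin of safety on lambda FLC depends on the SD staying near 9.09. Re-estimation is capped at 350, or 350 x 0.95 / 2 = 166 evaluable per arm. At an assumed SD of 12, t-test power there would be about 0.82, since 3.783/(12 x sqrt(2/166)) - 1.967 = 0.905. Adjustment would give about 0.84 or 0.87 at weight CV 10% or 15% with clearance independent of weight, and less otherwise. This is where the gain would be most useful.

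**What to change.** In SAP 17.1.2, with the change recorded in SAP section 4:

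- Derive the two-sided 95% CI for the difference in mean raw RR from a linear model with treatment, study site (the stratification factor, protocol 7.1.2) and screening dry weight. Mean QB over the last six sessions (note 3) is optional.
- Use the screening value. Visit 1 post-dialysis weight is measured after treatment and enters the RR formula.
- Keep the margins of -3.783 and -7.848; without an interaction term the model targets the same mean difference.
- Keep the blinded re-estimation on the raw one-sample SD. This is conservative, because the residual SD will be no larger apart from sampling error.
- Apply any normality check to the model residuals, and report the unadjusted t-test as supportive.
- In Sensitivity 3, state that dry weight is in the model that imputes missing RRs.

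The cost is SAP wording, with no new data or patients. Protocol 8.1 lets the SAP be finalised up to database lock. Because the trial is open-label, the covariates should be fixed before anyone sees RRs by arm.

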#### **7.2.1.3 Treatment Period (mid-week session)**

**(Note: Must be conducted within 2 weeks after randomization)**

During the mid-week treatment, the patient will undergo HD/HDF treatment, according to the according to the randomization number corresponding to the treatment group. Blood samples before dialysis should be collected as baseline data for patients. See Section 7.2.3 for detailed requirements for blood sample collection. All the following visit contents need to be collected before and after dialysis except for 24-h urine protein, which needs to be collected only before dialysis.

Parameter setting of HD/HDF treatment: QB  $\geq 250$  mL/min, QD  $\geq 500$  mL/min, QR (including UF)  $\geq 16$  L, treatment time: 4 hours.

Items tested at the Clinical Lab of Research Center.

---

- 1) Blood routine: Hematocrit , hemoglobin , mean corpuscular hemoglobin , mean corpuscular hemoglobin concentration , mean corpuscular volume , platelet count, red blood cell count, white blood cell count, eosinophil percentage;
- 2) Creatinine;
- 3) Blood urea nitrogen/blood urea;
- 4) CRP;
- 5) Electrolytes: P, K, Na, Ca, Cl
- 6) Liver function: ALT, AST, GGT, bilirubin, total bilirubin, total protein, globulin, albumin;

Items need to be tested at the Central Laboratory:

- 1)  $\beta$ 2-MG;
- 2)  $\alpha$ 1-MG;
- 3)  $\lambda$  FLC;
- 4)  $\kappa$  FLC;
- 5) YKL-4;
- 6) CFD;
- 7) Myoglobin;
- 8) Serum Albumin

Other visit assessments:

- 1) Vital signs: collect vital signs pre- and post-dialysis (according to various standard operating procedures): BP, pulse: pre- and post-dialysis; breathing rate and axillary temperature: Before dialysis treatment.
- 2) Body weight, dry weight (pre- and post-dialysis) ;
- 3) Treatment parameters: Dialysis date, start time and end time of each HD/HDF treatment, dialysis machine used, name of dialyzer, dialysate type and composition (sodium, bicarbonate, A concentrate used), preset QB, QD and ultrafiltration rate (QUF) (in mL/min), preset ultrafiltration volume (in L); actual total ultrafiltration volume at the end of treatment (unit: L); additional collection in control group: The preset amount of replacement fluid and the actual amount of replacement (unit: L); during the study visit, the QB should be recorded at the beginning of treatment and if there is any adjustment during the treatment; QD (mL/min) at the end of the treatment, and total dialysis time; The duration and reason of any treatment interruption;

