### **8.3 Significance Level and Power of Clinical Study**

A 0.025 one-sided significance level and a power of 90% were used in planning this study.

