### **8.5 Eligibility/Fail Criteria for Clinical Study Results**

Let  $\mu_T$  denote the Theranova 400 treatment mean and let  $\mu_R$  denote the FX 800 treatment mean. The statistical hypothesis of the study can be written as:

$$H_0: \mu_T - \mu_R \leq -\delta$$

$$H_a: \mu_T - \mu_R > -\delta$$

When evaluating the primary endpoint of  $\lambda$  FLC, the non-inferiority margin is -3.783 (10% of assumed mean RR of 37.83%). When evaluating the primary endpoint of  $\beta$ 2-MG RR, the non-inferiority margin is -7.848 (10% of assumed mean reduction ratio of 78.48%). When the non-inferiority of the two primary endpoints of  $\lambda$  FLC and  $\beta$ 2-MG RRs are both established, the non-inferiority of this study is established.

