## **8.7 Statistical Methods of all Data, together with Processing of Missing, Unused or Erroneous data (including midway exit and withdrawal) and Unreasonable Data**

### **8.7.1 Data Statistical Analysis**

#### **8.7.1.1 Analysis of Primary Endpoints**

For the  $\lambda$  FLC and  $\beta2$ -MG RR endpoints, let  $\mu_T$  denote the TheraNova 400 treatment mean and let  $\mu_R$  denote the FX 800 treatment mean. Then the null hypothesis to demonstrate non-inferiority using a 10% margin for  $\lambda$  FLC RR can be expressed as:  $H_0: \mu_T - \mu_R \leq -3.783$ . The alternative hypothesis is expressed as:  $H_a: \mu_T - \mu_R > -3.783$ . A t-test will be utilized to generate a two-sided 95% confidence interval (CI) for the difference in means ( $\mu_T - \mu_R$ ). If the lower bound of the CI is  $> -3.783$ , then non-inferiority between the TheraNova 400 and FX 800 treatment group can be demonstrated for  $\lambda$  FLC RR. If the lower bound of the CI  $> 0$ , then superiority of TheraNova 400 treatment over FX 800 treatment can be concluded.

Equivalently the null hypothesis to demonstrate non-inferiority using a 10% margin for  $\beta2$ -MG RR can be expressed as  $H_0: \mu_T - \mu_R \leq -7.848$ . The alternative hypothesis is expressed as:  $\mu_T - \mu_R > -7.848$ . A t-test will be utilized to generate a two-sided 95% confidence interval (CI) for the difference in means ( $\mu_T - \mu_R$ ). If the lower bound of the CI is  $> -7.848$ , then non-inferiority between the TheraNova 400 and FX 800 treatment group can be demonstrated for  $\beta2$ -microglobulin RR. If the lower bound of the CI  $> 0$ , then superiority of TheraNova 400 treatment over FX 800 treatment can be concluded.

Two sensitivity analysis will be conducted for both endpoints:

1. An ANOVA model with fixed effects for treatment group and study site to evaluate differences between the treatment groups will be analyzed and corresponding two-sided 95% CIs derived.

A non-parametric method: Wilcoxon Rank-Sum Test will be used to analyze the primary endpoints.

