### 3.2.3 Sample Size Calculation In Regard To $\beta 2$ -MG Reduction Ratio

A previously conducted Theranova HDF study was used to obtain  $\beta 2$ -MG RR mean and SD of 78.48 and 6.75; a higher estimate for SD of 14.28 is used to calculate sample size to

account for a potential increase in variability based on a literature review of studies conducted in China. Based on a 1:1 randomization, with a sample size of 75 patients in the Theranova 400 group and 75 patients in the FX 800 group (total N = 150), a Wilcoxon Rank-Sum test  $\alpha$  with a 0.025 one-sided significance level will have 90% power to demonstrate non-inferiority of the Theranova 400 Dialyzer compared to the FX 800 Dialyzer as assessed by  $\beta 2$ -MG RR with a non-inferiority margin of 10% (i.e. 7.848).

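### The primary t-test leaves out each solute's pre-dialysis concentration; adjusting for it could narrow the lambda FLC interval at almost no cost, by an amount the documents do not let us fix

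*SAP*

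**What the plan says.** Each co-primary endpoint is RR = (1 − Cpost/Cpre) × 100, with Cpost first corrected for fluid removal (Protocol 7.1.6.2.1; SAP 17.1.1). Protocol 7.2.1.3 lists lambda FLC and beta2-MG among the central-laboratory tests at the study session and says: "Blood samples before dialysis should be collected as baseline data for patients".

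The deciding analysis uses no covariate. Protocol 8.7.1.1: "A t-test will be utilized to generate a two-sided 95% confidence interval (CI) for the difference in means". SAP 17.1.2: "A two-sample t-test will be utilized to generate a two-sided 95% confidence interval (CI) for the difference in means". The lower limit is compared with −3.783 for lambda FLC and −7.848 for beta2-MG, and then with 0 for superiority.

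The analyses in SAP 17.1.3 do not use Cpre as a covariate either:

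- Sensitivity 1 is an ANOVA with treatment and site.
- Sensitivity 2 is a rank-sum test.
- Sensitivities 3 and 4 apply the t-test to imputed data. Age, gender, creatinine and BUN serve only to impute missing baseline values.

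Centre is the stratification factor for randomization (Protocol 7.1.2) but is also absent from the deciding test. Neither document gives a reason for omitting baseline adjustment.

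**The concern.** Dividing by Cpre is not the same as adjusting for it. The ratio removes the influence of starting level only if Cpost is exactly proportional to Cpre. If log Cpost rises with log Cpre with a slope other than 1, RR still varies with starting level, and the t-test counts that explainable variation as noise. The interval set against the margin would then be wider than necessary, and a chance difference in Cpre between arms would shift the estimate.

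The endpoint to watch is lambda FLC. It sets the sample size, and the trial succeeds only if both endpoints pass (Protocol 8.5; SAP 8.2).

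**Working it through.** **Inputs from the documents**

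- Error rate and power: "A 0.025 one-sided significance level and a power of 90% were used in planning this study" (Protocol 8.3).
- Lambda FLC margin: "the non-inferiority margin is -3.783 (10% of assumed mean RR of 37.83"%) (Protocol 8.5).
- Beta2-MG margin: "non-inferiority margin is -7.848 (10% of assumed mean reduction ratio of 78.48"%) (Protocol 8.5).
- Lambda FLC SD: "a higher estimate for SD of 9.09 is used by adding an additional +10% error to calculate sample size" (SAP 3.2.2). The uninflated value is 8.26.
- Beta2-MG SD: "a higher estimate for SD of 14.28 is used to calculate sample size" (SAP 3.2.3).
- True difference 0 (SAP 3.2.1), 129 evaluable per arm and 5% loss (SAP 3.2.4).

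**Step 1: reproduce the sample size.** For 90% power a t-test needs 123 per arm for lambda FLC and 71 for beta2-MG (noncentral t). The plan sizes for the rank-sum test, which under normality multiplies n by π/3:

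- 123 × 1.0472 = 128.8, so 129.
- 71 × 1.0472 = 74.4, so 75.
- 129/0.95 = 135.8, so 136 per arm and 272 in total.

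All three stated figures are reproduced.

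**Step 2: the planned t-test at 129 per arm.** For lambda FLC, SE = 9.09 × √(2/129) = 1.132. The 95% half-width is 1.969 × 1.132 = 2.229. The noncentrality is 3.783/1.132 = 3.342, giving power of 91.5%. For beta2-MG, SE = 1.778, half-width 3.50 and power 99.3%.

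**Step 3: add Cpre.** Let rho be the within-arm correlation between RR and log(Cpre). The residual SD becomes SD × √(1 − rho²), with one degree of freedom fewer. The documents do not give rho, so it is an assumption shown over a range. For lambda FLC with SD 9.09:

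| Assumed abs(rho) | Residual SD | CI half-width | Power |
|---|---|---|---|
| 0 (planned t-test) | 9.090 | 2.229 | 91.5% |
| 0.1 | 9.044 | 2.218 | 91.7% |
| 0.2 | 8.906 | 2.184 | 92.5% |
| 0.3 | 8.671 | 2.126 | 93.7% |
| 0.4 | 8.331 | 2.043 | 95.3% |
| 0.5 | 7.872 | 1.930 | 97.0% |

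The interval narrows by 1 − √(1 − rho²): 0.5% at 0.1, 4.6% at 0.3 and 13.4% at 0.5.

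At the uninflated SD of 8.26, power is 95.6% unadjusted, 97.0% at 0.3 and 98.8% at 0.5.

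Site terms cost little. With the 11 sites of Protocol 5.5, site and log(Cpre) together use 11 degrees of freedom. Even if site explained nothing, each power figure would fall by about 0.01 percentage point.

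**Step 4: what rho is plausible?** Write log Cpost = a + b·log Cpre + error. Then log(Cpost/Cpre) has slope b − 1 on log Cpre. The mean retained fraction is 100 − 37.83 = 62.17%, so the planning CV is 9.09/62.17 = 0.146. Hence abs(rho) ≈ (1 − b) × s/0.146, where s is the between-patient SD of log Cpre. Both b and s are assumptions:

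| s | b = 0.90 | b = 0.85 | b = 0.80 |
|---|---|---|---|
| 0.2 | 0.14 | 0.21 | 0.27 |
| 0.3 | 0.21 | 0.31 | 0.41 |
| 0.4 | 0.27 | 0.41 | 0.55 |

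At b = 1, rho is 0 and nothing is gained.

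**The case against.** The strongest reply is that nothing is wrong. Randomization makes the unadjusted difference unbiased, its type I error is correct, and the trial is sized for an unadjusted test. That stands. A reader might infer that leaving out Cpre biases the comparison or makes the planned test invalid; the documents give no support for that.

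A reader might also infer that the interval is certainly too wide. That would require showing that RR depends on Cpre within arm. The documents report no such correlation, and the endpoint already removes any proportional dependence. The claim must stay conditional.

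Third, one might read 91.5% as dangerously thin. The plan has three buffers:

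- The SD was raised from 8.26 to 9.09. If 8.26 is right, unadjusted power is already 95.6%.
- The sample size was computed for the rank-sum test, giving 129 per arm where the t-test needs 123.
- Blinded re-estimation at about half enrolment resets the sample size from the observed variance, up to 350 (Protocol 8.11; SAP 5.2). This covers a larger-than-planned SD up to that cap.

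These weaken any case for urgency. They do not remove the conditional gain: at a given sample size, a covariate that explains part of the RR variation still narrows the interval. Precision would also matter more if the assumed zero difference were optimistic. At a true lambda FLC difference of −1 point (an assumption), power is 69% unadjusted, 73% at rho 0.3 and 81% at rho 0.5.

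Finally, the change reaches beyond the SAP, because the protocol and its synopsis also name the t-test. That is correct and is counted in the cost.

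**Conclusion.** The point holds as an optional, low-cost gain in efficiency. A pre-treatment value that exists for every computable RR is used in no model as a covariate, and the plan gives no reason.

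For lambda FLC at the planning SD, the gain runs from 0.2 percentage points of power at rho 0.1 to about 5.6 at rho 0.5. At SD 8.26 it is about 1.4 points at 0.3 and 3.3 at 0.5. For beta2-MG power is not an issue. If RR is unrelated to Cpre, log(Cpre) costs one degree of freedom and brings nothing.

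These sizes rest on normal theory, 129 evaluable per arm, a true difference of 0 and an assumed rho. The documents do not show that the planned interval is in fact too wide, that the trial is underpowered, or that the t-test is wrong.

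**What to change.** In SAP 17.1.2, Protocol 8.7.1.1 and the synopsis, before treatment-level data are seen:

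- Estimate the difference in mean RR for each co-primary from a linear model with treatment, study site and log(Cpre) of that solute. Site is the stratification factor and is already in Sensitivity 1.
- Keep RR in raw percentage points. Without interaction terms the treatment coefficient is still a difference in mean RR, so the margins of −3.783 and −7.848 stand.
- Report the unadjusted t-test as supportive and keep the rank-sum analysis as Sensitivity 2. State what happens if normality fails, since the protocol's rank-based fallback cannot carry the covariate.
- Apply the same model in Sensitivities 3 and 4, which now inherit the t-test.
- Leave blinded re-estimation on the unadjusted pooled SD. This is conservative if the covariates explain any variance.

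The cost is SAP and protocol wording and a few degrees of freedom. The protocol change needs Ethics Committee approval (Protocol 14.3) and can go with the next amendment. No extra samples are needed, and no patient is lost from the primary analysis, because an RR cannot be computed without Cpre.
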